## **Approach**

### Study design

This is a prospective, randomized trial to determine whether a fixed dose of early basal insulin administration is superior to standard of care for the treatment of DKA.

#### Population

##### Inclusion Criteria

- Presented to Regions Hospital ED for chief complaint of DKA, nausea, vomiting, abdominal pain, hyperglycemia, or similar
- Meets all below diagnostic criteria for DKA per the American Diabetes Association:
  - Arterial or venous pH  $\leq$  7.3
  - Serum Bicarbonate  $\leq$  18 mEq/L
  - Ketonuria or ketonemia
  - Anion Gap  $>$  10
  - Blood sugar  $>$  250 mg/dL
- Receiving IV insulin infusion
- It is feasible to provide insulin glargine within 2 hours (+/- 30 minutes) of IV infusion start
- Will be admitted to the ICU for DKA, or already admitted to the ICU for DKA
- Ability to provide informed consent

### Exclusion Criteria

- Age  $<$  18
- End stage renal disease or hepatic disease
- Hypotension requiring IV vasopressors or inotropes at any point during admission (i.e. norepinephrine, dobutamine, vasopressin, etc.)
- Need for emergent surgery
- Pregnant patients
- Prisoners
- Indication for insulin therapy other than DKA (hypertriglyceridemia, beta-blocker overdose, hyperglycemia without DKA)
- Patients receiving prior to admission insulin pump therapy
- Patients receiving prior to admission combination insulin products (i.e. Novolin® 70/30, Novolog® 70/30, Humalog® 75/25, etc.)
- Did not consent to study

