## Study aims

Primary Outcome:

- 1) Does early administration of insulin glargine result in a shorter ICU length of stay when compared to usual care for the treatment of diabetic ketoacidosis?

Hypothesis: Early administration of insulin glargine will result in shorter ICU length of stay when compared to usual care in patients with DKA.

Secondary Outcomes:

- 1) Does early administration of insulin glargine result in a shorter hospital length of stay (defined as time between start of insulin infusion and discharge from hospital) when compared to usual care for the treatment of diabetic ketoacidosis?

Hypothesis: Early administration of insulin glargine will result in shorter hospital length of stay when compared to usual care in patients with DKA.

- 2) Does early administration of insulin glargine result in a faster recovery from DKA (defined as blood glucose < 200 and two of: Anion Gap  $\leq$  12, Serum Bicarbonate  $\geq$  15 mEq/L, or pH > 7.3) when compared to usual care for the treatment of diabetic ketoacidosis?

Hypothesis: Early administration of insulin glargine will result in a faster recovery from DKA (defined as blood glucose <200 and two of: Anion Gap  $\leq$  12, Serum Bicarbonate  $\geq$  15 mEq/L, or pH > 7.3) when compared to usual care for the treatment of diabetic ketoacidosis.

- 3) Does early administration of insulin glargine result in a shorter duration of elevated anion gap (defined as time with anion gap > 12) when compared to usual care for the treatment of diabetic ketoacidosis?

Hypothesis: Early administration of insulin glargine will result in a shorter duration of elevated anion gap (defined as time with anion gap > 12) when compared to usual care for the treatment of diabetic ketoacidosis.

- 4) Does early administration of insulin glargine result in a shorter duration of time on IV insulin infusion when compared to usual care for the treatment of diabetic ketoacidosis?

Hypothesis: Early administration of insulin glargine will result in a shorter duration of time on IV insulin infusion when compared to usual care for the treatment of diabetic ketoacidosis.

- 5) Does early administration of insulin glargine result in a lower prevalence of rebound hyperglycemia, defined as blood glucose > 180 mg/dL in the 24 hours after IV insulin infusion discontinuation, when compared to usual care for the treatment of diabetic ketoacidosis?

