## **Screening and Enrollment**

### Screening

Because CCRC research interns provide 24/7 ED coverage, and ED pharmacy is also covered 24/7, there is no restriction as to the time of day or day of week when enrollments can take place. However, to enhance investigator oversight, patients will only be enrolled when specific ED Pharmacists are on shift, who are the primary investigators. This includes [name], [name], and [name]. If those pharmacists are not at the site, the patient will not be enrolled.

ED pharmacists received an Epic alert any time a patient meeting DKA criteria is admitted to the ED. The pharmacist will alert the CCRC research intern to confirm inclusion/exclusion and approach the patient for study participation. CCRC interns will also watch the ED track board for patients admitted with a chief complaint of DKA, nausea, vomiting, abdominal pain, hyperglycemia, or similar. Alternatively, an ED pharmacist or attending physician will notify Research of a potential patient by calling the 24/7 intern bat phone.

Labs: in order to confirm inclusion/exclusion criteria, the patient will need to have had the following labs completed (*which are standard of care for any patient with DKA on the differential diagnosis. These are not extra labs that the study investigators want, rather, they will already be collected by any provider for any patient with presumed DKA*):

- Arterial or venous pH  $\leq 7.3$
- Serum Bicarbonate  $\leq 18$  mEq/L
- Presence of ketonuria or ketonemia (beta-hydroxybutyrate  $> 0.27$  mmol/L)
- Anion Gap  $> 10$
- Blood sugar  $> 250$  mg/dL

All patients who present with symptoms of possible DKA should receive these labs under standard of care, per Regions Hospital DKA Protocol. Should any of these labs be missing, the patient will not be eligible for the study.

The research intern will confirm inclusion and exclusion criteria using a RedCap screening checklist, and obtain permission from the patient’s attending to approach for study consent.

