### Randomization

An Excel file with rows numbered 1 through 150 will be populated with a randomization column. Using Excel randomization functions, a research staff member who will not be involved in consenting will assign either the number 1 (control) or 2 (intervention) to each row number, ensuring 75 of each are populated. We chose the number 150 based on the expected sample size of 132, plus extras in case of higher-than-expected enrollment. The research staff member will then black out (black highlight over black font) the randomization column, so other team members are blinded to future assignments. Upon consent of an eligible patient, research staff will enter subject information in the next available row, and randomization status will be unblinded by removing the black highlight for that row only.

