### Enrollment

Once the patient is randomized, the CCRC intern will notify the ED pharmacist who will determine if patient is currently taking basal insulin and, if they are taking basal insulin prior to admission, will verify the home basal dosing. CCRC research staff will be notified of the dosing order from the randomization and will place the appropriate order. The patient will either receive 0.2 u/kg insulin glargine, current (prior to admission) basal insulin dose, or no additional treatment study protocol. CCRC staff will abstract the study data points from the patient’s EMR while the patient is in the Emergency Department, throughout their hospital stay, and again at the time of discharge. The ED pharmacist will time the insulin glargine dose to be administered optimally within two hours after initiation of the IV insulin infusion.

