### Variable list, sources, and data collection

The variables listed on the below data collection form will be incorporated into a secure REDCap database that research staff will use to enter the data. Patients will be assigned study ID numbers in the REDCap database. The REDCap database will contain identifying information, however, if de-identified data needs to be shared outside of the direct study team, the dataset can be downloaded without identifying variables such as MRN.

Variable Name	Role of Variable	Measurement Scale
Study ID	Unique identifier	Continuous (001 – n)
MRN	Link to EMR	String
Full name	Link to EMR	String
Date of ED presentation	Link to EMR	DMY
Age	Descriptive	Continuous
Race	Descriptive	Categorical, as reported in Epic
Ethnicity	Descriptive	Categorical, as reported in Epic
Sex at birth	Descriptive	Categorical, as reported in Epic
End stage renal disease or hepatic disease	Inclusion/exclusion criteria	Binary
Vasopressor dose to treat hypotension at any point during admission	Inclusion/exclusion criteria	Binary
On insulin pump therapy at baseline (prior to ED)	Inclusion/exclusion criteria	Binary
On combination insulin products (i.e. Novolin® 70/30, Novolog® 70/30, Humalog® 75/25, etc.) at baseline	Inclusion/exclusion criteria	Binary
Presenting pH (prior to intervention)	Inclusion/exclusion criteria	Continuous

Time of first pH	Calculate time to resolution	Continuous
Time of short-acting insulin start	Calculate time to resolution	Continuous
Time of first pH > 7.3	Outcome Calculate time to resolution	Continuous
Presenting blood glucose in mg/dL	Inclusion/exclusion criteria	Continuous
Time of first blood glucose < 250 mg/dL	Outcome Calculate time to resolution	Continuous
Blood glucose > 180 mg/dL in the 24 hours after IV insulin infusion discontinuation	Outcome	Binary
Blood glucose < 70mg/dL $\geq$ 1 time at any point while on IV insulin therapy or in the 24 hours after IV insulin infusion discontinuation	Outcome Prevalence of AE (hypoglycemia)	Binary
Blood glucose < 70mg/dL at any point between glargine start and 24 hours after IV insulin infusion discontinuation (control group only)	Outcome Prevalence of AE that may be contributable to study intervention (hypoglycemia)	Binary
Mean blood glucose in 24 and 48 hours after IV insulin infusion discontinuation	Outcome	Continuous
Presenting anion gap	Inclusion/exclusion criteria	Continuous
Time of first anion gap	Calculate time to resolution	Continuous

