### **Risks and Benefits**

Potential risks to the patient include hypoglycemia with the administration of both basal and regular insulin administration, however, no study that has examined early basal insulin in combination with IV insulin has shown an increase in the risk of hypoglycemia. Standard of care for patients with DKA includes an overlap of basal and regular insulin for approximately two hours; this ensures that the basal insulin has time to start working before stopping the regular insulin. In our study, patients will have a longer duration of overlap of basal and regular insulin as the basal insulin will be given earlier in the patient's treatment course. Patients with DKA who are receiving IV insulin

infusions, whether participating in this study or not, undergo frequent blood glucose monitoring and have the IV insulin infusion titrated appropriately to prevent hypoglycemia. Potential benefits to the patient and society include shorter hospital and ICU lengths of stay, faster time to resolution of DKA, and less rebound hyperglycemia.

For study patients randomized to the SOC group, the only potential for change in standard care would be if a provider who *would* have deviated from the Regions Hospital DKA Protocol were the patient not in the study *does not* deviate from it if the patient is in the study, due to education about the importance of adhering to the SOC DKA Protocol. (For example, a physician might give SC glargine before the patient meets all criteria for it in the DKA Protocol.) However, as the DKA Protocol is evidence-based, peer-reviewed, and created for optimal patient safety and outcomes, this should not be considered a risk. If, for whatever reason, a study patient in the SOC arm needs treatment that directly contradicts the SOC DKA Protocol, the patient will be withdrawn from the study to ensure patient care and safety are the first priority. In looking at existing data to inform this study protocol, only 3 of 45 patients with DKA at Regions Hospital received SC glargine prior to what the protocol dictates.

All adverse events and serious adverse events will be reported to the IRB within the required time windows.

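### The vasopressor exclusion covers the whole admission, so it cannot be assessed at randomization, and no analysis-set rule prevents its later use to drop randomized patients

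*Combined protocol and SAP*

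**What the plan says.** The Exclusion Criteria list "Hypotension requiring IV vasopressors or inotropes at any point during admission". The table under Variable list, sources, and data collection carries a matching binary field, "Vasopressor dose to treat hypotension at any point during admission", whose role is given as inclusion/exclusion.

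Eligibility is settled early. The Inclusion Criteria require that "It is feasible to provide insulin glargine within 2 hours (+/- 30 minutes) of IV infusion start". Under Screening, "The research intern will confirm inclusion and exclusion criteria using a RedCap screening checklist", and this comes before the approach for consent. Under Randomization, "Upon consent of an eligible patient, research staff will enter subject information in the next available row", and the assignment for that row is then revealed. Under Enrollment, staff go on abstracting the record "throughout their hospital stay, and again at the time of discharge".

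The primary question in Study aims is "Does early administration of insulin glargine result in a shorter ICU length of stay when compared to usual care". The Statistical analysis plan names tests for each outcome. It defines no analysis population, makes no intention-to-treat statement, and gives no rule for a patient found ineligible after randomization. The only removal after randomization that the plan describes is in Risks and Benefits: if a standard-of-care patient needs treatment that contradicts the hospital DKA protocol, "the patient will be withdrawn from the study to ensure patient care and safety are the first priority".

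**The concern.** The criterion depends on the whole admission, but eligibility is decided in its first hours. A patient randomized at hour 2 who first needs a vasopressor on day 2 was eligible when randomized and meets an exclusion criterion by discharge. The plan does not say whether that patient counts.

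The choice matters for three reasons. Vasopressor need after randomization could be affected by treatment. It plausibly goes with a long ICU stay, so dropping these patients selects on something close to the primary outcome. They would also leave the between-arm comparison of hypoglycemia (secondary outcome 6), which Risks and Benefits names as the potential risk of giving both insulins. No placebo or blinding of treating staff is described, so a decision left until analysis could be made with arm and outcome in view.

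**Working it through.** **Order of events**

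1. Screening checklist, then consent, then randomization, then glargine. The target is 2 h from infusion start with a 30-minute tolerance, so randomization falls within about 2.5 h.
2. The vasopressor criterion can be completed only at discharge.
3. In the variable list, the pH eligibility field is limited to before the intervention and the insulin-pump field to before the ED visit. The vasopressor field has no such limit and repeats the whole-admission wording.
4. Abstraction runs to discharge, so later vasopressor use will be visible.

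Staff following the criterion and field literally would drop the day-2 patient. Staff following the screening sequence would keep the patient. The Statistical analysis plan does not settle it.

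**The plan's own figure**

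Inputs from Sample size: 66 per arm, coefficient of variation 0.6, alpha 0.05, 80% power. The two-sided test is from the Statistical analysis plan.

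- Log-scale SD = √ln(1 + 0.6²) = 0.5545.
- Detectable ratio = exp[(1.960 + 0.842) × 0.5545 × √(2/66)] = 1.31, as stated. Power at 1.31 is 79.9% by the normal approximation and 79.3% by the noncentral t.
- If 6.5 h is 31% of the shorter stay, that stay is 6.5/0.31 = 21.0 h and the longer is 21.0 × 1.31 = 27.5 h.

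**Loss of numbers**

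Sample size takes exclusions off before enrollment (264 less 25% and another 25% = 132) and allows for none afterwards. If a share of each arm were removed later (an assumed share), noncentral-t power at 1.31 would be 78.5% at 2%, 77.2% at 5% and 74.9% at 10%. This loss is minor.

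**Bias**

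Assumptions, none of them in the documents: the vasopressor rates below; stays 3 times as long for these patients; control mean 27.5 h for the others. The mean of an arm is then 27.5 × (1 + 2 × rate), divided by 1.31 in the intervention arm where an effect is assumed. With rates of 2% and 8% and ratio 1.31:

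- control: 27.5 × 1.04 = 28.6 h
- intervention: 27.5 × 1.16 / 1.31 = 24.4 h
- difference, all randomized: 4.2 h
- difference after removal: 27.5 − 27.5/1.31 = 6.5 h

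The rejection rates below are from a simulation of the Wilcoxon test with 66 per arm and 4,000 runs. Its mean differences agree with the arithmetic to within 0.1 h.

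| Rate, control / intervention | Other effect | Control minus intervention, all randomized | After removal | Rejection, all randomized | After removal |
|---|---|---|---|---|---|
| 5% / 5% | none | 0 h | 0 h | 4.8% | 5.2% |
| 5% / 5% | 1.31 | 7.2 h | 6.5 h | 71.9% | 74.2% |
| 2% / 8% | none | −3.3 h | 0 h | 8.0% | 5.1% |
| 2% / 8% | 1.31 | 4.2 h | 6.5 h | 52.8% | 74.6% |
| 8% / 2% | 1.31 | 10.1 h | 6.5 h | 86.5% | 75.5% |

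After removal the answer is 6.5 h (or 0 h with no other effect) whatever the vasopressor rates are. The comparison can no longer see a difference in deterioration, in either direction. With equal rates, type I error stays near 5%.

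**The case against.** The strongest reply is that the criteria are applied at screening. The checklist comes before consent, only eligible patients are approached, and the accrual arithmetic takes exclusions off before the 132. On that reading the criterion means vasopressor use so far. The eligibility label in the variable list is shared with ordinary screening items, and nothing there says that the field triggers removal. The one withdrawal rule in Risks and Benefits does not mention vasopressors. This much stands: a reader might infer that later-deteriorating patients are removed and the longest ICU stays lost, but no section orders the first and no figure supports the second. The reply does not dispose of the point, because the wording covers the whole admission and no analysis-set rule closes the gap.

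A reader might also infer a large bias. Taking the 21.0 h above as a geometric mean gives an arithmetic mean of 21.0 × √1.36 = 24.5 h. Removing k of 66 patients from one arm, with an assumed stay L, lowers its mean by k(L − 24.5)/66. For L of 96 to 120 h that is 2.2 to 2.9 h with k = 2 and 3.3 to 4.3 h with k = 3, or one third to two thirds of 6.5 h. The documents do not support that as an estimate. The stays and counts are assumed, and there is no stated reason why removal should fall on one arm only. Sample size does not say whether its length of stay is ICU or hospital stay.

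The plan also expects a Wilcoxon test. On the rank scale, a ratio of 1.31 gives P(X > Y) = Φ(0.270/(0.5545 × √2)) = 0.635, which is 0.135 above one half. Removing the top 2 or 3 of 66 from one of two otherwise equal arms shifts it by k/132 = 0.015 or 0.023, only about 11% to 17% of that effect.

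Finally, a bad course would not go unreported: Risks and Benefits sends all adverse and serious adverse events to the IRB. Only the comparison between arms is exposed.

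**Conclusion.** The concern holds as a defect in the definition of who is analysed. The criterion cannot be assessed at randomization. Applied as written, it would exclude randomized patients on a later event that treatment might affect and that plausibly goes with long ICU stays, and the Statistical analysis plan has no rule that prevents this. It is not shown that such removal is planned.

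The size is unknown, because the documents give neither a vasopressor rate nor a stay for these patients. With equal rates the bias is small. With unequal rates removal hides the difference: under the assumed 2% and 8% rates and threefold stays it would erase a 3.3 h disadvantage, or turn a 4.2 h advantage into 6.5 h. With the rates reversed it would understate the benefit. Equal rates cannot be taken for granted when treatment may affect the event. The correction is therefore worth making before outcome data are reviewed by arm.

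**What to change.** 1. **Exclusion Criteria:** limit the vasopressor and inotrope criterion to the period before randomization.
2. **Variable list:** split the field into use before randomization (eligibility) and use after randomization (descriptive and safety).
3. **Statistical analysis plan:** state that all randomized patients are analysed in their assigned arm for all outcomes. Say that this includes patients who later need vasopressors or inotropes, and standard-of-care patients withdrawn under Risks and Benefits, as far as consent to data use allows. That withdrawal rule applies to one arm only, so changing the eligibility line alone would leave it open. The clinical decision to depart from the DKA protocol is untouched; only the handling of the patient's data is specified.

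The cost is one criterion line, one REDCap field and a sentence or two of analysis plan, with no extra patients or tests. The downside is that a few long stays remain and add some variance. In the equal-rate illustration (5% per arm, ratio 1.31), rejection is 71.9% with all randomized patients against 74.2% after removal.

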### Sample size

From 1/1/2018 to 6/30/2019 there were 399 unique encounters of patients admitted to Regions Hospital with an associated ICD-10 code of E10.10 (Type 1 diabetes mellitus with ketoacidosis without coma), E10.11 (Type 1 diabetes mellitus with ketoacidosis with coma), E11.10 (Type 2 diabetes mellitus with ketoacidosis without coma),

E11.11 (Type 2 diabetes mellitus with ketoacidosis with coma), E13.10 (Other specified diabetes mellitus with ketoacidosis without coma), or E13.11 (Other specified diabetes mellitus with ketoacidosis with coma).

We expect patients to present at the same rate, indicating that an estimated 264 patients with one of these eligible diagnoses will present over the twelve months of study enrollment. Of those 264, we expect 25% to be ineligible due to meeting one of the study exclusion criteria and another 25% to be eligible but decline participation. Therefore, we expect to see 132 total eligible subjects (66 in each randomization arm). Due to our fixed sample-size, in lieu of a traditional power analysis to determine the number of subjects needed to detect a difference between the group we plugged our fixed sample size into a power analysis and solved for length of stay.

We ran a power analysis using the same historical data used under the Sample size section of this proposal. Because we expect about 132 patients to be enrolled, we inspected length of stay (LOS) from the first 100 cases in our historical data. LOS is heavily right-skewed, so we log-transformed it to estimate detectable effect size. We used the “proc power” program in SAS 9.4, which has specifications for comparing two log-transformed means. In order to achieve 80% power to detect a true difference between two fixed groups of  $n=66$ , the ratio of logs would have to be about 1.31; when normalized, this translates to about 6.5 hours ( $\alpha = 0.05$ , coefficient of variation = 0.6). So, with our sample size, we estimate that the intervention would need to cause a 6.5-hour difference in average length of stay between groups in order for us to detect a difference 80% of the time.

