### **Setting/Environment/Organizational feasibility**

The study will be conducted at Regions Hospital. The study will primarily take place while the patient is in the ED, but the study intervention may take place in the ICU if the patient is quickly admitted. The ED pharmacists can oversee ICU medication orders, and the ICU pharmacists will also be trained about this study. This location is appropriate as this study is designed to assess the efficacy and safety of early basal insulin administration versus standard of care for the treatment of DKA. The department heads for endocrinology, emergency medicine, critical care, internal medicine and pharmacy were contacted and have endorsed providing support for this study. The Department of Endocrinology was consulted on providing recommendations for both the dosing of basal insulin as well as the timing of basal insulin initiation in relation to starting the IV insulin infusion. Furthermore, the ED pharmacists, ICU pharmacists, and floor pharmacists have a close working relationship, and communicate with each other daily. All three study investigators have spent time working as ICU pharmacists.

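### The expected 132 patients, and the 80% power for 6.5 hours that rests on them, include no allowance for the rule that patients enroll only when one of the specified pharmacists is on site

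*Combined protocol and SAP*

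**What the plan says.** The Sample size section starts from all coded DKA admissions to the hospital, with no limit on hour or day, and projects "an estimated 264 patients with one of these eligible diagnoses will present over the twelve months of study enrollment". It then makes two deductions: "we expect 25% to be ineligible due to meeting one of the study exclusion criteria", and "another 25% to be eligible but decline participation". What remains is the expected sample: "Therefore, we expect to see 132 total eligible subjects (66 in each randomization arm"). The power calculation takes this number as fixed and solves for the effect: "we estimate that the intervention would need to cause a 6.5-hour difference in average length of stay between groups", for 80% power, at a two-group ratio of about 1.31, alpha 0.05 and a coefficient of variation of 0.6.

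The Screening section first notes that interns and ED pharmacy are present around the clock, then narrows this: "patients will only be enrolled when specific ED Pharmacists are on shift, who are the primary investigators". Three people are listed, and the consequence of their absence is explicit: "If those pharmacists are not at the site, the patient will not be enrolled". The Setting/Environment/Organizational feasibility section also counts three: "All three study investigators have spent time working as ICU pharmacists".

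The Randomization section carries 132 forward and adds spare rows, up to 150, for enrollment above expectation. Strengths and limitations presents round-the-clock pharmacist availability, and enrollment across every shift, as a strength of the study.

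**The concern.** Presence of a specified pharmacist is not in the Exclusion Criteria list, and a patient who arrives when none is there has not refused. As worded, neither 25% covers such patients. The projection from 264 to 132 therefore treats every eligible, willing patient as enrollable at whatever hour they arrive.

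The plan does not choose N to reach a target. It predicts N from accrual and reports what that N can detect. The 80% and the 6.5 hours are its only statement of what the trial can show, and both depend on 132. If fewer patients enroll, a null result on length of stay could be read as evidence against a 6.5-hour effect that the trial had appreciably less than 80% power to find.

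**Working it through.** **Inputs.** From Sample size: 399 encounters in 18 months, 264 expected in twelve months, deductions of 25% and 25%, 66 per arm, ratio 1.31, CV 0.6, alpha 0.05, 80% power, 6.5 hours. From the statistical analysis plan: a two-tailed test. From Screening: the pharmacist rule, with three people listed. From Timeline: 13 month columns marked for enrollment. Not in the documents: the share *f* of otherwise enrollable patients who can be enrolled under the pharmacist rule. It is varied below.

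**Step 1: reproduce the plan.**
- Accrual: 399/18 × 12 = 266, close to the stated 264; 264 × (1 − 0.25 − 0.25) = 132.
- Log-scale SD: √ln(1 + 0.6²) = 0.5545. Effect: ln 1.31 = 0.2700.
- Noncentrality at 66 per arm: 0.2700 / (0.5545 × √(2/66)) = 2.80. Two-sided power from the noncentral t is 79.3%; the ratio detectable with 80% power is 1.313.

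The stated figures reproduce. The calculation is right if 132 enroll.

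**Step 2: insert the missing factor.** N = 264 × 0.5 × *f* for 12 months, multiplied by 13/12 for 13 full months. Power is at ratio 1.31 by the same method.

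| Assumed *f* | 12 months: N | Power | Ratio at 80% power | 13 months: N | Power |
|---|---|---|---|---|---|
| 1.00 | 132 | 79% | 1.31 | 143 | 82% |
| 0.90 | 119 | 75% | 1.33 | 129 | 78% |
| 0.80 | 106 | 70% | 1.36 | 114 | 73% |
| 0.71 | 94 | 65% | 1.38 | 102 | 68% |
| 0.50 | 66 | 50% | 1.47 | about 72 | 53% |

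The 0.71 row illustrates three people each working 40 hours a week without overlap, with arrivals spread evenly: 120/168 = 0.714.

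**Step 3: convert to hours.** The plan does not give the reference stay behind 6.5 hours. At ratio 1.31, 6.5 hours implies a mean of 6.5/0.31 = 21.0 h in the shorter-stay arm, or equivalently 6.5/(1 − 1/1.31) = 27.5 h in the longer-stay arm. Holding one or the other fixed, the 12-month detectable difference is 6.9–7.0 h at *f* = 0.90, 7.2–7.5 h at 0.80, 7.6–8.0 h at 0.71, and about 9–10 h at 0.50.

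**Step 4: the dosing window.** The Inclusion Criteria allow glargine within 2 hours (± 30 minutes) of the start of the infusion, so some patients whose infusion starts shortly before a covered shift could still be enrolled. How many depends on the shift pattern, which is not given. With 120 covered and 48 uncovered hours a week, and 2 to 2.5 hours regained per gap, *f* rises from 0.71 to 0.76–0.77 if the gaps last 12 hours, 0.79–0.80 if 8 hours, and 0.86–0.89 if 4 hours. For 8-hour gaps, for example: (120 + 6 × 2)/168 = 0.786.

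**The case against.** The strongest reply is that no stated figure has been shown to be wrong: the subtraction and the power both check, and coverage is unknown. That is correct. The point concerns an unstated assumption in the enrollment count, and the documents do not show how far it fails.

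A second reply is that the plan calls its sample size fixed, so slow accrual might cost time and not power: 12/*f* months to reach 132, for example 15 months at *f* = 0.80. But N is itself derived from twelve months of accrual, and nothing says that enrollment continues until 132 is reached. If that is the intention, the duration needs restating in place of the power.

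Third, the Timeline may allow 13 months. If these are 13 full months, the shortfall at 90% coverage nearly disappears (129 patients, 78% power). The extra month restores 132 only if *f* is at least 12/13, about 92%. Thirteen columns could also come from twelve months that start mid-month.

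Fourth, enrollment across every shift can mean that no type of shift is barred, with the specified pharmacists rotating through all of them. That reading is possible, so the conflict with Screening may be loose wording, but it needs a clarifying sentence.

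A reader might also infer that full coverage demands 168/3 = 56 hours a week from each of three people and is therefore impossible. The documents do not support that. The figure assumes even arrivals and no use of the dosing window, and the rota is not given.

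**Conclusion.** The concern holds as an omission. The pharmacist rule restricts enrollment, is covered by neither deduction, and is not allowed for elsewhere; the spare randomization rows protect only against over-enrollment. The 132 patients, 80% power and 6.5 hours are correct only if essentially every eligible, consenting patient can be enrolled under the rule.

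The direction is clear: on the plan's twelve months, any enrollable share below 100% lowers expected N and power. The size is not known. The range of 75% power at 90% coverage to 50% at 50% coverage is hypothetical. It assumes twelve months, the plan's own CV and ratio, and the two deductions as stated; a thirteenth full month adds about 3 points to each figure. The hours carry a further uncertainty because the reference stay is not stated.

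A reader might infer that the trial is underpowered by a definite amount, or that the power formula is at fault. The documents support neither.

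**What to change.** - Multiply expected enrollment by the share of DKA presentations that can be enrolled under the pharmacist rule, taken from the rota and allowing for the dosing window.
- State the enrollment duration used, so that Sample size and Timeline can be read together.
- Restate N, power, and the detectable ratio and hours on that basis.
- Reconcile the claim about enrollment on every shift in Strengths and limitations with the rule in Screening.
- If the intention is to enroll until 132 is reached, say so, and restate the enrollment duration in place of the power.

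The cost is a look at the rota, a short recalculation and some wording; no visits or data items are added. The downside is that the stated power, or the duration, will probably be less favorable.
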